**Tolcapone Treatment of Obsessive Compulsive Disorder:
A Double-Blind, Placebo-Controlled, Cross-Over Pilot Study**

NCT03348930

Version Date: 26AUG2020

[name].

University of Chicago

Project Goals

The goal of the proposed study is to evaluate the efficacy and safety of tolcapone in adults with obsessive compulsive disorder (OCD). The hypothesis to be tested is that tolcapone will be more effective and well tolerated in adults with OCD compared to placebo. The proposed study will provide needed data on the treatment of a disabling disorder where current treatments are often ineffective.

Specific Aims

The primary aim of this application is to conduct a randomized placebo-controlled pharmacotherapy trial using tolcapone in 20 participants with OCD. The study will consist of two phases: a 2 week active treatment phase with tolcapone, a one-week wash-out phase, and a 2 week placebo phase. The subjects will be randomized to either receive tolcapone or placebo treatment in the first 2 weeks, and the other during the remaining 2 week phase.

This will be one of few studies assessing the use of pharmacotherapy for the treatment of OCD in adults. Assessing the efficacy and safety of tolcapone will help inform clinicians about additional treatment options for adults suffering from this disorder.

Several brain structures and functions have been implicated in OCD. Studies have consistently shown hyperactivity in the orbitofrontal cortex and caudate (1-2). Other key implicated regions (suggesting abnormalities in functional or structural connections) include the anterior cingulate cortex, thalamus, amygdala, and parietal cortex (3-5). Neuropsychological studies involving patients with OCD have shown deficits in cognitive abilities that are linked to the functioning of the frontal lobe and its related frontosubcortical structures, such as executive functioning, impulsivity in motor function, and cognitive inflexibility (i.e., not changing behavior on the basis of new information) (6-7).

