All subject data will be maintained by the study personnel under the supervision of the principal investigator. All subjects will be seen in the Department of Psychiatry at the University of Chicago Medical Center at [name]. Patient binders will be kept in a locked room only accessible to research staff.

Finance and Insurance

All research will be paid for by the internal departmental funds of the Department of Psychiatry at the University of Chicago. In the event that this research activity results in an injury, treatment will be available, including first aid, emergency treatment and follow-up care as needed. Care for such injuries will be billed in the ordinary manner to the subjects' insurance company. If the subject believes that they have suffered a research related injury, they will be instructed to inform the principal investigator immediately.

Compensation

The study will consist of 4 visits. For participating in the study, participants will receive \$25 per visit to be paid in the form of a check at the completion of the study. Parking vouchers will also be provided for subjects as-needed.

[figure not shown]
Time Line

Recruitment for the proposed study will begin as soon as study drug is available. It is anticipated that all subjects would be entered into the study within approximately 12 months, and that the study would be completed within 15 months of initiation.

Study Design

The study is a 5-week, double-blind, placebo-controlled, pilot study of the safety and efficacy of tolcapone for adults with OCD. All eligible study subjects will go through a 2-week treatment phase during which they will begin tolcapone at 100mg twice a day. Subjects will be

given a matching placebo during the 2-week placebo phase. Subjects will be seen for scheduled study visits every two weeks during the 2-week blinded phases. Subjects will be randomized to either receive either the active or placebo condition during the first 2-week phase, and the remaining condition during the second 2-week phase. Study timeline is outlined below.

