All efficacy and safety assessments will be performed at each visit. Subjects who are not compliant with their use of study medication (i.e. failing to take medication for three or more consecutive days) will be discontinued from the study. Patients who experience a clinically significant adverse event will also be discontinued from the study. Liver diseases will be assessed at the time of subject entry and at the last visit. Subjects will have their blood drawn at baseline and again at the time of study completion to test for liver function.

Due to the pandemic of COVID19, study participants can perform their baseline and follow-up visits online using encrypted Zoom instead of in person visits. All inventories will be assessed. Blood samples, however, will be at the discretion of the study PI. In cases where they are considered medically necessary, the participant can have them drawn locally and submitted to the study team.

Screening Assessments

1. Demographic data and clinical characteristics will be recorded for each subject (baseline visit).
2. Formal screening psychiatric interview for each subject including the Mini International Neuropsychiatric Inventory (24) (baseline visit).
3. Symptom severity at baseline and follow-up visits will be examined using reliable and valid scales:
 - a. *Yale Brown Obsessive Compulsive Scale* (YBOCS) (25) (each visit)
 - b. *Clinical Global Impression severity and improvement scales* (26) (each visit)
 - c. *Sheehan Disability Scale* (27) (baseline and final visit)
 - d. *Hamilton Anxiety Rating Scale* (HAM-A) (28) (each visit)
 - e. *Hamilton Depression Rating Scale* (HAM-D) (29) (each visit)

Yale Brown Obsessive Compulsive Scale (YBOCS) (25). The YBOCS is a reliable and valid 10-item clinician administered scale assessing urge, behavior, and total severity scores.

Clinical Global Impression- Severity and Improvement (CGI) (26). The CGI consists of a reliable and valid 7-item Likert scale used to assess severity and improvement in clinical

symptoms. The CGI severity scale was used at each visit and ranges from 1 = “not ill at all” to 7 = “among the most extremely ill.” The CGI Improvement scale was used at each follow-up visit and ranges from 1 = “very much improved” to 7 = “very much worse.”

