Sheehan Disability Scale (SDS) (27). The SDS is a three-item, reliable and valid self-report scale that assesses functioning in three areas of life: work, social or leisure activities, and home and family life. Scores on the SDS range from 0 to 30.

Hamilton Anxiety Rating Scale (HAM-A) (28). The HAM-A is a reliable and valid, clinician-administered, 14-item scale that provides an overall measure of global anxiety.

Hamilton Depression Rating Scale (HAM-D) (29). The HAM-D is a valid and reliable, 17-item, clinician-administered rating scale assessing severity of depressive symptoms.

Cognitive Assessments: In addition, subjects will undergo cognitive assessments at baseline. Assessments of cognitive control will be comprised of several valid paradigms (Table 1). These tasks are designed to probe dissociable neural circuitry and cognitive processes likely to be implicated in the pathophysiology of OCD. Task order will be chosen arbitrarily and will be applied consistently across subjects, to minimize possible confounding factors of differences in task order across participants.

Table 1. Neurocognitive Tasks

Task	Target Cognitive Process
MOT	Training Task.
Intra-dimensional/Extra-dimensional Set Shift Task (ID/ED task)	Intra- and extra-dimensional thinking ability. Assesses cognitive flexibility.
Stop-Signal Task of Inhibitory Control	Motor impulsivity and response inhibition.
Tower of London Task	Problem solving and logic task.
Cambridge Gamble Task	Decision making and risk adjustment.

RVP	Visual processing abilities.
SWM	Spatial working memory abilities.

Efficacy Assessments

The primary outcome measure will be the *Yale Brown Obsessive Compulsive Scale (YBOCS)*. The YBOCS is a reliable and valid scale that is frequently used in research to assess symptom severity.

Secondary efficacy measures include

- *The Clinical Global Impression-Improvement and Severity scales (CGI)*
- *Sheehan Disability Scale (SDS)*
- *Hamilton Anxiety Rating Scale (HAM-A)*
- *Hamilton Depression Rating Scale (HAM-D)*.

Safety Assessments

Safety assessments (sitting blood pressure, heart rate, adverse effects, and concomitant medications) will be documented at each visit.

Suicidality will be assessed using the Columbia Suicide Severity Rating Scale. This scale will be performed at every visit. Subjects who endorse suicidal thoughts at any time during the study will be removed from the study and appropriate clinical intervention (e.g. hospitalization) will be arranged.

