Liver diseases will be assessed at the time of subject entry and during the final study visit. Subjects will undergo a blood draw by venipuncture. One 8ml sample will be collected for liver function testing. This procedure will be repeated at the time of study completion, during the subject's final visit.

The investigator will record use of concomitant medications in terms of daily dosage, start and stop dates, and reason for use. Adverse events will be recorded at each study visit and as they become known to the study staff. Medication compliance will be ascertained through weekly pill count of investigational medication.

Risks and Benefits

Risks

Tolcapone has been associated with hepatic failure in some individuals and carries a Black Box warning of hepatotoxicity from the FDA. Given the tolcapone dose of 200mg/day

used in this study is far lower than the 600mg/day dose used in Parkinson's disease and the dose associated with hepatotoxicity, and the fact that participant is only taking the medication for 2 weeks, we feel that the risk of hepatotoxicity is very low. Hepatotoxicity associated with tolcapone has been documented when the medication has been used continuously for at least 16 weeks at total daily doses of 600mg/day and liver function tests were not monitored (30).

Patients will also be assessed for clinical signs of hepatic dysfunction (persistent nausea, fatigue, lethargy, anorexia, jaundice, dark urine, and pruritus).

Other common adverse events associated with tolcapone (nausea, diarrhea, orthostatic hypotension, somnolence, confusion, hallucinations, and rhabdomyolysis are possible, although these have been reported at the dosage used for Parkinson's disease (300-600mg/day) and not the lower dose proposed for this study.

Benefits

Potential benefits include a possible direct medical benefit. Specifically, the study drug may help curb the severity of symptoms related to OCD, but there can be no guarantee that this will be the case. As current options may provide little benefit for many people with OCD, the current study could offer significant advancement in possible treatments for this disorder.

Data Analysis

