Demographic and baseline visit characteristics for tolcapone and placebo groups will be compared using chi-square and analysis of variance to determine if group differences existed at randomization. Given the crossover design, both the placebo and the active tolcapone groups will contain an N of 20. Primary and secondary measures will be examined using repeated-measures ANOVA modeling analyses (PROC MIXED, SAS/STAT Software for Windows, Version8.2, SAS Institute Inc., Cary, NC, USA). The baseline value of the measure being analyzed will be used as a covariate. A time trend (linear) will be included in all models. The difference in the overall level of posttreatment values, the main effect for treatment, will be the test of primary interest. Analyses will be performed on all available data as well as for the completers. All available post-randomization data will be first analyzed and a secondary, supportive analysis of completers will be performed. All comparison tests will be two-tailed and an alpha level of .05 will be used to determine statistical significance given the exploratory nature of the study.

Ethical Considerations

This study will be conducted according to US and international standards of Good Clinical Practice (FDA regulations 21 CFR 312 for IND studies and FDA guidance E6) for all studies. Applicable government regulations and University of Chicago research policies and procedures will also be followed. This protocol and any amendments will be submitted to the

University of Chicago Institutional Review Board (IRB) for formal approval to conduct the study. The decision of the IRB concerning the conduct of the study will be made in writing to the investigator.

REFERENCES

2. Baxter LR Jr, Phelps ME, Mazziotta JC, Guze BH, Schwartz JM, Selin CE. Local cerebral glucose metabolic rates in obsessive-compulsive disorder: a comparison with rates in unipolar depression and in normal controls. *Arch Gen Psychiatry* 1987;44:211-218

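### Blood pressure is read only in the sitting posture, so asymptomatic or unreported falls on standing would be missed, although orthostatic hypotension is among the tolcapone risks the protocol names

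*Combined protocol and SAP*

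**What the plan says.** The visit-level safety measures are in the Safety Assessments section: "Safety assessments (sitting blood pressure, heart rate, adverse effects, and concomitant medications) will be documented at each visit". Suicidality ratings and liver tests are described separately. Adverse events have a second route, later in the same section: "Adverse events will be recorded at each study visit and as they become known to the study staff". How they are elicited is not stated, and no prompt for symptoms on standing is given.

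The Risks section, after discussing the liver, continues: "Other common adverse events associated with tolcapone (nausea, diarrhea, orthostatic hypotension, somnolence, confusion, hallucinations, and rhabdomyolysis are possible". It then adds: "although these have been reported at the dosage used for Parkinson's disease (300-600mg/day) and not the lower dose proposed for this study". The dose appears in Study Design, where participants enter the active phase and "they will begin tolcapone at 100mg twice a day". The Risks section gives the same dose as a daily total of 200 mg.

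Two further statements bear on what can be collected. Under the COVID-19 provision in Study Design, "study participants can perform their baseline and follow-up visits online using encrypted Zoom instead of in person visits", with no procedure for blood pressure at such visits. Data Analysis notes that "both the placebo and the active tolcapone groups will contain an N of 20", because each participant is to receive both treatments. Project Goals makes safety a goal alongside efficacy.

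**The concern.** Orthostatic hypotension is a fall in pressure on standing. The protocol names it as possible and takes blood pressure at each visit, but in one posture only. A participant with an unremarkable sitting value and a marked drop on standing would have nothing abnormal in the blood pressure record. If no symptom was felt or reported, the drop would appear nowhere in the trial's data.

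What is at stake is the completeness of the safety information at 200 mg/day. Sitting values could later be cited as blood pressure safety data at this dose, although they say nothing about the postural effect. The crossover gives each participant a tolcapone phase and a placebo phase, which suits a within-person comparison of postural change, but the plan does not collect the measurement for it.

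**Working it through.** The plan states no figure to reproduce. The check is mainly a comparison of sections.

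1. **What is measured.** Every mention of blood pressure, posture and vital signs was looked for. The only measurement specified is the sitting one in Safety Assessments. There is no standing, supine or postural-change reading.

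2. **What the named risk requires.** For one participant at one visit, postural change = standing pressure − sitting pressure. The plan supplies only the second term. Any sitting value is compatible with any postural change, so the change cannot be recovered from the planned data.

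3. **What else could reveal it.** Adverse effects are documented at visits and between visits, in both phases. A drop that produces a reported symptom can therefore be recorded and compared between tolcapone and placebo. What remains unseen is the asymptomatic or unreported drop.

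4. **Whether the dose qualifier closes the gap.** The study dose is 2 × 100 = 200 mg/day. Against the range in the Risks section, 200/300 = 0.67 of the lower end and 200/600 = 0.33 of the upper end. These ratios show that the dose is lower. They do not give a risk, because the documents contain no rate at any dose and no dose-response data. The qualifier is a reason to expect fewer events, but the same sentence still calls them possible. The protocol does not elsewhere treat a low expected risk as a reason not to measure. It judges the hepatotoxicity risk very low at this dose and duration, yet plans liver tests at entry and at the final visit (at the principal investigator's discretion under the COVID-19 provision).

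5. **What an added reading could deliver at best.** With 20 participants, all measured on tolcapone and none showing a drop, the one-sided 95% upper bound on the rate is 1 − 0.05^(1/20) = 13.9%. This is a ceiling on the information gained. Online visits and discontinuations would reduce the number measured and raise the bound. Under the present plan no such bound can be given for postural drops, because the share that would come to notice is unknown.

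**The case against.** The strongest case against is that nothing here contradicts itself. The protocol never says that the sitting reading is there to detect orthostatic hypotension. The Risks sentence lists seven events, and no dedicated measurement is named for the others either, rhabdomyolysis included. All seven are described as reported at higher doses than the one used here. This is a 20-person pilot with two weeks on drug, and adverse events are recorded throughout.

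Much of this stands, and it keeps the point small. It does not remove it. Blood pressure is already being taken, so for this event a second reading with the same cuff is enough.

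A reader might infer that the trial cannot detect orthostatic hypotension at all, or that only a spontaneously volunteered symptom would reveal it. The documents do not support either reading: adverse effects are documented at each visit, and nothing says that collection is passive. A reader might also infer that the comparison with placebo is lost for this event. Only the comparison of measured postural change is absent; symptomatic events can be compared across phases. Nor do the documents say what sitting pressures on tolcapone would look like, so it cannot be claimed that they will appear normal.

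The remedy has its own limits. Visits are every two weeks, which gives about one end-of-phase reading per person on each treatment. Without control of time since dose, that reading could also miss a drop.

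**Conclusion.** The point holds as a minor one. The blood pressure measurement in Safety Assessments does not match a risk named in the Risks section, and a plan followed exactly would miss asymptomatic or unreported postural drops. This rests on the definition of orthostatic hypotension and on the absence of any second posture in the documents, not on an assumed event rate. The number of drops missed cannot be stated: the documents give neither the frequency of the event nor the share that is symptomatic. The consequence is confined to safety ascertainment at 200 mg/day. The primary YBOCS comparison is untouched, and no conclusion follows about whether the drug is safe or unsafe at this dose.

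**What to change.** Reconcile Safety Assessments with Risks as follows.

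- **Measurement.** At each in-person visit, record sitting and then standing blood pressure and heart rate, the standing values at a fixed interval after standing that the investigators set in advance. Record the difference.
- **Online visits.** Mark the postural reading as not done, so that a missing value is not read as normal.
- **Analysis.** Add a sentence to Data Analysis: describe, within person, the postural change at the end of the tolcapone phase against that at the end of the placebo phase, and report the number of pairs. This is at most 20, and fewer with online visits or discontinuations. Description is enough at this size.

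The cost is a few minutes per in-person visit, with the same cuff and staff, and extra fields on the case report form. The change concerns measurement only; it proposes no dose, stopping or treatment rule.

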The proposed study will consist of a 5-week double-blind cross-over study trial of tolcapone in 20 people (ages 18-65). The study will be divided into an initial 2 week phase and a second 2 week phase, with one of the 2 week phases consisting of active treatment with tolcapone, and the other 2 week phase consisting of inactive placebo treatment. There will be a one-week wash-out phase between the 2-week treatment phases. Participants will be randomized to receive either tolcapone or placebo during the first 2 week phase on a 1:1 basis. This blinding will be maintained by the IDS pharmacy at the University of Chicago.

Based on a recent single dose tolcapone study for OCD, we should not need longer than two weeks to see an effect (unpublished data). Tolcapone is not an SSRI, so we don't anticipate it taking as long as an SSRI to see an effect. In a study using tolcapone for gambling disorder, effects were shown within the first two weeks of taking the drug (Grant et al., 2013). We do not have enough data to know what the effect size will be. It will likely be underpowered, but 20 active vs. 20 placebo should be sufficient to detect a signal. This will provide data for a future well-powered study.

Subjects:

Inclusion criteria:

- 1) Males and females age 18-65;
- 2) Diagnosis of current OCD based on DSM-5 criteria and confirmed using the clinician-administered Structured Clinical Interview for DSM-5 (SCID);
- 3) Able and willing to provide written consent for participation.

Exclusion criteria:

- 1) Unstable medical illness, including liver disease, as determined by the investigator and liver function test;
- 2) History of seizures;
- 3) Clinically significant suicidality (defined by the Columbia Suicide Severity Rating Scale);
- 4) Baseline score of ≥ 17 on the Hamilton Depression Rating Scale (17-item HDRS);

- 5) Lifetime history of bipolar disorder type I or II, schizophrenia, autism, any psychotic disorder, or any substance use disorder;
- 6) Initiation of psychotherapy or behavior therapy within 3 months prior to study baseline;
- 7) Previous treatment with tolcapone;
- 8) Any history of psychiatric hospitalization in the past year;
- 9) Currently pregnant (confirmed by urine pregnancy test)

Data Handling and Record Keeping

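### Does the plan need to say how an end-of-washout YBOCS enters the primary model, and which groups are compared at baseline?

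*Combined protocol and SAP*

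**What the plan says.** The Methodology section describes 20 people taking each treatment for two weeks. It adds: "There will be a one-week wash-out phase between the 2-week treatment phases". On allocation it says: "Participants will be randomized to receive either tolcapone or placebo during the first 2 week phase on a 1:1 basis".

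The Compensation section gives four visits. Study Design spaces visits two weeks apart within the blinded phases and calls for every efficacy measure at each visit. Screening Assessments lists the YBOCS at each visit and places the diagnostic interview at the baseline visit.

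Data Analysis begins: "Demographic and baseline visit characteristics for tolcapone and placebo groups will be compared using chi-square and analysis of variance", the purpose being to see whether groups differed at randomisation. The next sentence reads: "Given the crossover design, both the placebo and the active tolcapone groups will contain an N of 20". The model is a repeated-measures mixed model, adjusted for each measure's value at baseline and carrying a linear term for time. The section identifies its main comparison as follows: "The difference in the overall level of posttreatment values, the main effect for treatment, will be the test of primary interest".

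The section then names two analyses, one on all available data and one on completers, and gives their order: "All available post-randomization data will be first analyzed and a secondary, supportive analysis of completers will be performed".

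**The concern.** The visit rules suggest a YBOCS at the end of washout, when nobody is on study medication. Such a value is post-randomisation, so a literal reader would put it in the primary model. It belongs to neither treatment, and the plan gives no coding rule. The analyst could attach it to the treatment just finished, to the treatment about to start, or to placebo. Each choice gives a different expected treatment effect, and one can produce an apparent effect when there is none. The primary estimate is meant to inform a later study, so an error in either direction would mis-size that study.

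The baseline comparison looks wrong for a simpler reason. If both groups hold the same 20 people, a test between them can never show a difference and says nothing about how randomisation turned out.

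**Working it through.** **1. Visit schedule.** Phases of 2 + 1 + 2 = 5 weeks, four visits, and an interview held at the baseline visit point to weeks 0, 2, 3 and 5. The timeline figure is not shown, so this is an inference.

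**2. The plan's own count.** Twenty participants each taking both treatments gives 20 and 20, as stated. Allocation at 1:1 gives two sequences of about 10. If the same 20 people were entered as both groups, every group mean and proportion would coincide: F = 0, chi-square = 0, p = 1 for any data.

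**3. End-of-phase values only (weeks 2 and 5).** The estimate is half the difference between sequences in mean (week 2 − week 5). Let δ be the drug effect and g any common change between the phases. The tolcapone-first mean is δ + g and the placebo-first mean is −δ + g. Half the difference is [δ + g − (−δ + g)]/2 = δ, a ratio of 1.00. Placebo response cancels. With two outcome times the linear trend is the period effect. A week-0 covariate is constant within a person and leaves the complete-data estimate unchanged. This assumes no residual drug effect reaches week 5.

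**4. Week 3 coded to a neighbouring treatment.** Assume equal variances and a common correlation r, and set k = r/(1 + 2r). Let z be the between-sequence difference in treatment codes at weeks 2, 3 and 5, and m the difference in means as a share of δ. Then

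ratio = (Σzm − k·Σz·Σm) / (Σz² − k·(Σz)²).

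- Preceding treatment, full washout: z = (1, 1, −1), m = (1, 0, −1). At r = 0.5, k = 0.25 and the ratio is 2/(3 − 0.25) = 0.727. At r = 0.7, k = 0.292 and it is 2/2.708 = 0.738.
- Following treatment, full washout: z = (1, −1, −1) gives the same values.
- Half the drug effect retained, m = (1, 0.5, −1), r = 0.5: preceding (2.5 − 0.125)/2.75 = 0.864; following (1.5 + 0.125)/2.75 = 0.591.
- With a week-0 covariate the residual correlation is r/(1 + r). For r = 0.5 this is 0.333, so k = 0.2 and the full-washout ratio is 2/2.8 = 0.714.

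**5. Week 3 coded as off-drug, with linear week.** The model combines two sources of information. The sequence contrast at weeks 2 and 5 has information 1 (in common units) and estimates δ. The average treatment code, (½, 0, ½), has a second component after removal of the mean and the linear trend. Its sum of squares about the mean is 1/6. The part explained by week is (1/6)²/(14/3) = 1/168. The remainder is 27/168 = 0.1607, doubled for two sequences to 0.3214. Its weight is 0.3214/1.3214 = 0.243 at every r.

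- A placebo response P present on treatment but lost in washout makes the second source estimate δ + 2P. The result is δ + 0.486P: ratio 1.243 for P = 0.5δ and 1.486 for P = δ.
- With δ = 0 and P of −1.5 or −3 points, the expected estimate is −0.73 or −1.46. In 100,000 simulated trials with an assumed SD of 6 and r from 0.5 to 0.7, the false-positive rate was 9–11% or 19–28%.
- Half the drug effect retained and no placebo response: 0.757 + 0.243 × 0.5 = 0.878.
- Full washout and no placebo response lost: 1.00, with standard error √(1/1.3214) = 0.87 of that from weeks 2 and 5 alone.

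**6. Where the off-drug bias comes from.** With visit as a category, or washout as its own level, the average profile is fully absorbed and only the sequence contrast remains. The ratio is then 1.000 in all the carryover and placebo-response cases above. The bias needs off-drug coding and the linear term together.

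**7. Which reading the text supports.** The sentence on post-randomisation data repeats the contrast in the sentence before it, all available data against completers, so it concerns who is analysed. The test itself is on posttreatment values, and 20 per condition fits one end-of-phase value per person per treatment. The protocol names tolcapone, placebo and washout as three distinct phases, so coding washout as placebo has no basis in it. Baseline refers elsewhere to the single entry visit, which makes the week-0 value the natural covariate.

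**The case for a change.** The strongest case for a change is that two competent analysts could follow the same paragraph and report different primary estimates, with the choice still open once the data are seen. Across the codings tried, the expected estimate runs from 0.59 to 1.49 of the true effect. Two or three sentences would close the question without new data.

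Part of this stands. No sentence assigns a role to a washout-end YBOCS, the baseline covariate is not explicitly tied to week 0, and the baseline groups are loosely named. If baseline meant each phase's own starting value, week 3 would be a covariate instead of an outcome, and the estimate could differ.

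The range, however, comes from codings that the text does not suggest. The low end needs an off-drug value labelled with the treatment about to begin, plus half the drug effect retained. The high end needs washout labelled as placebo, a linear trend over three visits, and a placebo response as large as the drug effect that vanishes within a week. The documents supply no value for any of these quantities. A missing figure may also settle the visit's purpose, so its absence cannot be held against the plan.

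**Conclusion.** No change follows. The week-3 point is a gap that an analyst fills sensibly: taking the end-of-phase values as outcomes, or giving washout its own level, returns 1.00 of the true effect in every case tried. Naming period and the week-0 covariate would spell out the model already implied without altering the complete-data estimate. The departures (0.59–0.87 for neighbouring-treatment coding, 0.88–1.49 for off-drug coding) are illustrative. They depend on the inferred visit weeks, equal variances, correlations of 0.5 to 0.7 and the assumed carryover and placebo response.

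The baseline sentence is a slip of wording. It speaks of differences at randomisation, and randomisation is to the first-phase treatment, so the groups intended are tolcapone-first and placebo-first, about 10 each. The count of 20 per condition fits the efficacy analysis described next. The comparison does not enter the primary test, and correcting its wording would change no efficacy result. This is also an exploratory pilot that the protocol itself expects to be underpowered.
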